7.2.2 Sampling technique

This study will use the convenience sampling technique due to the ease of inviting/recruiting patient participants that have been referred for an pelvis MRI for a rectum study. It is expected that there will not be any bias from this sampling technique that would cause the sample results to be skewed from the patient group population.

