2 RATIONALE

One of the disadvantages in MRI is that acquisition times can be lengthy, making it likely that patient movement whilst in the scanner will affect image quality and making it more difficult for patients to complete their MRI scan (Hollingsworth et al. 2015). In recent years, waiting lists of patients referred for MRI have also been at an all-time-high as a result of the COVID-19 pandemic (GOV.UK, 2023).

To tackle this backlog, manufacturers have developed Artificial Intelligence (AI) image reconstruction (DLR) techniques that compensate for the poor image quality that results when using higher accelerating/parallel imaging factors during MRI scanning (Magnetom Flash, 2021). This also has the potential to improve patient compliance.

These DLR techniques are still relatively new and require a number of resources including radiographer, radiologist and clinical scientist support to optimise the technique. Consequently, implementation across the NHS has been slow and has therefore not yet been validated on rectum MRI protocols. Therefore, the aim of this study is to demonstrate that DLR techniques can be implemented in rectum MRI protocols, as well as provide recommendations for its implementation.

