6 STUDY SETTING

This is a single centre study at St George's Hospital with three MRI scanners that each have up-to-date software versions with DLR functionality. Healthy volunteers will be recruited for initial optimisation of the DLR enabled rectum protocol and will be recruited from within St George's Hospital's Medical Physics and Clinical Engineering (MPCE) group via an email on the joint mail base.

It will be explained to volunteers that images will be reviewed in the context of image quality assessment. In the event of an incidental finding, the volunteer's GP will be notified. A volunteer will not be scanned if they do not provide details of their GP, NHS number, and do not give consent to being scanned. Any volunteer that is vulnerable, not an adult, is/may be pregnant or has any other contraindications to MRI will be immediately excluded from this study. All volunteer images will be stored on PACS and accessed only by [name], [name], [name] or any other delegate listed on the delegation log. These images will be stored for up to 10 years following completion of the study, unless a participant wishes for them to be deleted at an earlier date.

Validation will need to be carried out on adult patients referred to St George's Hospital's General Radiology MRI department for an MRI pelvis scan for a rectum study. This research setting is appropriate since there are approximately 200 patients who are referred for a pelvis MRI each year, with patients also having follow-up scans throughout their care.

Potential participants will be identified by the Radiology Information System (RIS) and their suitability will be assessed. Any patient that is vulnerable, not an adult, is/may be pregnant or has any other contraindications to MRI will be immediately excluded from this study.

Once a patient's suitability has been approved, they will be invited to take part by post and a participant information sheet (PIS) will be provided (e.g. in person, via email or post). The potential participant will be provided with the contact details of the researchers ([name] and [name]) if they have any questions.

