7.1.1 Inclusion criteria

Staff in the Medical Physics and Engineering group, plus adult patients that have been referred to St George's Hospital General Radiology MRI department for an MRI pelvis study and able to withstand up to an additional 15 minutes in the MRI scanner will be considered for participation in this study.

The ability for volunteers and patients participating in this study will not be dependent on:

- Gender.
- Ethnicity.
- Socio economic grouping.
- Clinical condition.
- Location.

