7.1.2 Exclusion criteria

Any volunteer that is not an adult; and is/or may be pregnant, will be excluded from this study.

Any patient that cannot give informed written consent, cannot complete a screening questionnaire, is not an adult; has not been referred for an MRI pelvis scan for a rectum study at St George's Hospital General Radiology MRI department as an outpatient; is an at-risk patient; and is/or may be pregnant, will be excluded from this study.

Non-English speakers will be excluded from this study as informed consent cannot be guaranteed and questions the participants may have may not be satisfactorily answered.

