7.3.1 Participant identification

Healthy volunteers are needed initially to optimise a rectum protocol enabled with DLR. Members of the MPCE group at St George's Hospital will be invited to volunteer in this study via an email to the joint MPCE mail base by [name] or [name]. If a volunteer is suitable for participating,

they will be provided with a PIS that details the purpose and their role in the study. If volunteers wish to proceed, they must provide details of their GP, NHS number, and complete a written consent form a volunteer screening form.

A list of healthy volunteers from the MPCE group that wish to participate in this study will be maintained and include their full name, work email address, when they were last screened and if they have provided written consent. This will be maintained by [name] and [name]. Any volunteers that fail to meet the inclusion criteria or meet any exclusion criteria will not be included in this study.

Validating the DLR technique requires imaging patients with or suspected of having rectal cancer, who will be identified using the trust's RIS. This will be carried out by [name], [name] and/or [name] who will search on RIS for patients referred for a pelvis MRI for a rectum study. If suitable patients are identified, they will be invited to take part in the study and provided with a PIS through the post with ample time to read the information and consult family members/friends/legal representatives. If the patient wishes to proceed with participating in the study, informed written consent will be obtained and noted on Soliton. This invitation will be sent by [name] or [name].

A list of patients approached to participate in this study will be maintained to ensure their eligibility onto the study has been checked and recorded, and to avoid inviting a patient who had previously turned down the study invitation.

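### Section 7.2.2 expects no bias from convenience sampling without giving a reason; the protocol fixes no invitation order, and eligibility selects on a trait that may change the DLR-minus-routine difference

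*Protocol*

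**What the plan says.** Section 7.2.2 of the protocol names the method and the reason for it: "This study will use the convenience sampling technique due to the ease of inviting/recruiting patient participants". The next sentence states the expectation: "It is expected that there will not be any bias from this sampling technique that would cause the sample results to be skewed". The comparison it draws is with the patient group population. No argument or data supports it.

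Two sections describe how patients are reached. Section 6: "Potential participants will be identified by the Radiology Information System (RIS) and their suitability will be assessed". Section 7.3.1: "If suitable patients are identified, they will be invited to take part in the study". Neither gives an order of invitation, and neither says what suitability means beyond the stated criteria. Section 7.3.1 also provides a record: "A list of patients approached to participate in this study will be maintained".

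Eligibility is set elsewhere. Section 7.1.1 requires patients to be "able to withstand up to an additional 15 minutes in the MRI scanner will be considered for participation". Section 7.1.2 limits the study to outpatients, excludes at-risk patients and those who cannot give written consent, and adds: "Non-English speakers will be excluded from this study".

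Section 2 gives the motive for faster imaging. Long acquisitions make movement likely to affect image quality, as well as "making it more difficult for patients to complete their MRI scan".

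**The concern.** Two separate gaps lie between the patients scanned and the patients to whom the result will be applied, and the no-bias sentence covers both without argument.

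The first is the sampling technique itself. With no invitation order and an undefined suitability check, the protocol does not prevent some eligible patients from being approached and others passed over. Nothing that must be recorded would show whether this happened, because the 7.3.1 list covers only patients who were approached.

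The second is eligibility. The design compares two scans in the same patient, which removes differences between patients in their general level of image quality. It does not remove differences between patients in how much DLR changes the image. Section 2 links scan length to movement and to completing the scan, and section 7.1.1 selects on tolerance of extra scan time. The trait being selected on is therefore a plausible modifier of the quantity being estimated.

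At stake is the scope of the conclusion. Section 4.1 sets out to validate the DLR protocol on clinical rectum studies, and section 5 ends in a judgement on whether DLR suits clinical rectum protocols. Both targets are wider than the sample.

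**Working it through.** **The plan's own figure first.** Section 7.2.1 gives 24 patients per half (two-sided Wilcoxon signed-rank, dz 0.8, alpha 0.05, power 0.95). Using a noncentral t with n scaled by the asymptotic relative efficiency 3/π:

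- scaled n = 24 × 0.955 = 22.92
- noncentrality = 0.8 × √22.92 = 3.83
- power = 0.955, and 24 is the smallest n that reaches 0.95
- (24 × 2) / (1 − 0.20) = 60 patients, and 60 + 15 = 75

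The figures reproduce. This point does not depend on them, and nothing below changes them.

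**Steps between referral and analysis.**

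1. *Referral.* Section 6 gives about 200 patients a year referred for pelvis MRI.
2. *Search and suitability.* Staff search RIS and assess suitability (sections 6 and 7.3.1). No order and no further definition are given. This step belongs to the sampling technique.
3. *Eligibility.* Tolerance of up to 15 more minutes (7.1.1); outpatient, English-speaking, not at-risk, able to consent (7.1.2). This step is not part of the sampling technique and would stay the same under consecutive or random invitation.
4. *Consent.* Voluntary. No rate is given.

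The 7.2.2 sentence speaks only of the technique, so step 2 is what contradicts it directly. But it claims likeness to the patient group population, and step 3 also separates the sample from that population.

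**Why pairing does not settle it.** Let D be a patient's DLR-minus-routine difference. Suppose a share f of referred patients is left out, and their mean D differs by d from the mean m among those included. Then:

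- population mean = (1 − f) × m + f × (m + d) = m + f × d
- error of the sample mean = f × |d| in size

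The error is zero only if f = 0 or d = 0. Pairing makes neither of these zero.

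**Size.** The protocol gives neither f nor d. As an illustration only, assume f from 0.1 to 0.3 and |d| from 0.5 to 2 Likert points:

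- smallest: 0.1 × 0.5 = 0.05 points
- middle: 0.2 × 1 = 0.2 points
- largest: 0.3 × 2 = 0.6 points

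The sign may be either. Patients who tolerate scanning poorly might gain more from a shorter acquisition, or their DLR images might be worse. The calculation concerns a mean, whereas the primary outcome in section 4.2 compares medians, so it shows the mechanism and does not predict the trial's result.

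**The case against.** The strongest reply is that the protocol does not say staff pick among eligible patients. Sections 6 and 7.3.1 can be read as inviting each suitable patient found, and the ease mentioned in 7.2.2 can be read as easy access to people already referred. Section 7.1.1 also says participation does not depend on gender, ethnicity, socio-economic grouping, clinical condition or location. This stands: a reader might infer that staff choose the easiest patients, but the text shows only that nothing prevents it.

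A reader might also infer that eligibility removes the patients most prone to movement. No criterion names movement. The criterion is tolerance of added time, which is unavoidable when DLR sequences are appended to the routine scan; its link with movement is a plausible reading of section 2. The explicit exclusion for movement, in section 7.2.1, applies after scanning. It is a separate question about the analysis set.

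The eligibility limits are openly stated and would survive any change of sampling technique, so consecutive invitation alone does not widen the population. This also stands, and is why the scope statement is needed as well.

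Nor does the sampling fraction show bias. Sixty of about 200 is 30%, or 36% of about 167 if referrals fall evenly over ten months (assumption), but most samples leave most of their population out. If 60% to 80% of referrals were eligible (assumption), 36% enrolled would mean that at least 45% (0.36/0.80) to 60% (0.36/0.60) of eligible patients had to be invited, which limits the room for choice without removing it.

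Finally, section 4 calls this a local validation project, and reporting of patient flow is commonly left to later documents. That lowers the weight of the point. It does not supply a reason for the expectation in 7.2.2, which the protocol itself states.

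**Conclusion.** The point holds in a limited form. The no-bias expectation in section 7.2.2 is unsupported. It sits beside an invitation process with no fixed order, an undefined suitability check, and eligibility rules that select on scan tolerance. The paired difference may vary with tolerance, and the within-patient design does not protect against that.

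A reader might go further and infer that the result cannot be applied to the referred population, or that it will flatter DLR. The protocol supports neither. Selection matters only if the DLR-minus-routine difference varies with the selected traits, and no figure in the protocol shows whether it does or in which direction. The 0.05 to 0.6 point range rests wholly on assumed inputs. The correct statement is that applicability beyond the sampled patients is not shown and should not be presumed.

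No endpoint, test or sample size is affected. What changes is how patients are invited and what the trial may claim.

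**What to change.** - In 7.2.2, replace convenience sampling with consecutive invitation of every eligible rectum referral in RIS date order, until both halves of the DLR protocol have their patients.
- Delete the no-bias sentence. State instead that conclusions apply to English-speaking outpatients, not at-risk, who can tolerate the extended scan.
- Extend the 7.3.1 list to patients identified but not invited, with the reason, so that selection can be described from the list.

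The eligibility criteria can stay as they are. The cost is protocol wording, a few more postal invitations and some extra log entries, with no added patients or staff. Consecutive invitation addresses the sampling step only; the scope statement deals with the eligibility limits.

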7.3 Recruitment

This section details the participant eligibility screening process for this study and includes the methods used to identifying eligible participants/sample.

7.3.1 Participant identification

Healthy volunteers are needed initially to optimise a rectum protocol enabled with DLR. Members of the MPCE group at St George's Hospital will be invited to volunteer in this study via an email to the joint MPCE mail base by [name] or [name]. If a volunteer is suitable for participating,

they will be provided with a PIS that details the purpose and their role in the study. If volunteers wish to proceed, they must provide details of their GP, NHS number, and complete a written consent form a volunteer screening form.

A list of healthy volunteers from the MPCE group that wish to participate in this study will be maintained and include their full name, work email address, when they were last screened and if they have provided written consent. This will be maintained by [name] and [name]. Any volunteers that fail to meet the inclusion criteria or meet any exclusion criteria will not be included in this study.

Validating the DLR technique requires imaging patients with or suspected of having rectal cancer, who will be identified using the trust's RIS. This will be carried out by [name], [name] and/or [name] who will search on RIS for patients referred for a pelvis MRI for a rectum study. If suitable patients are identified, they will be invited to take part in the study and provided with a PIS through the post with ample time to read the information and consult family members/friends/legal representatives. If the patient wishes to proceed with participating in the study, informed written consent will be obtained and noted on Soliton. This invitation will be sent by [name] or [name].

A list of patients approached to participate in this study will be maintained to ensure their eligibility onto the study has been checked and recorded, and to avoid inviting a patient who had previously turned down the study invitation.

7.3.2 Consent

The participant will receive an invitation to the study, as well as a PIS that clearly explains their participation in the study is completely voluntary, they have the right to withdraw from the study at any time, and their responsibility whilst on the study. The participant will be provided with the PIS at least 24 hours before the scan so that they have enough time to read the PIS in its entirety and contact the researchers if they have any follow-up questions. This will also be reiterated to the participant on the day of their scan.

The PIS will ensure that the patient:

- Understands the purpose of the study.
- Understands their responsibility whilst participating in the study.
- Understands the benefits, risks and burdens of their participation in the study.
- Understands that they may withdraw from the study at any time without the need to give a reason for doing so.
- Understands that they do not have to participate in the study and that their care will not be affected.
- Understands that the MR images collected in this study will be stored on St George's
 Hospital's computer network/PACS and that their medical history/results related to their MRI
 may need to be accessed.
- Understands that their MR images may be used in a scientific publication and that these will
 not contain any images that can be used to identify them.

Once the participant has reviewed the PIS and understood the points above, then informed written consent will be obtained from the participant.

Consent provisions for collection and use of participant data and biological specimens

No biological specimens will be taken as part of this study. The data that concerns the healthy volunteers from the MPCE group will include their full name, date of birth, NHS number, GP, height and weight. Additionally, their images will be stored on the Trust's PACS system.

Patient participants will also have the same details stored/accessed; however, this information is accessed as part of their care and so no additional patient identifying information is accessed that would not have been otherwise.

If a patient participant wishes to withdraw from the study, permission will be sought to use any images acquired up till that point. If permission by the patient is denied, their information will not be accessed and their images will not be used in the study.

7.3.3 Data collection tool

Case Report Forms will be designed by the CI and or PI.

On paper CRFs all data should be entered legibly in black ink. If the Investigator makes an
error, it will be crossed through with a single line in such a way to ensure that the original entry
can still be read. The correct entry will then be clearly inserted. The amendment will be
initialled and dated by the person making the correction immediately. Overwriting or use of
correction fluid will not be permitted.

The Staff Delegation of Responsibilities Log should identify all trial personnel responsible for data collection, entry, handling and managing the database.

Data that will be recorded directly into the CRF and contain:

- Patient details (name, DOB, NHS number and/or MRN)
- Confirmation of their eligibility including date
- Study ID
- Written consent form signed by the participant
- Signed notes made by the investigator with time and date recorded
- Withdrawal form (if necessary) with date and time recorded.

This study will not handle any biological samples. However, information recorded in patients' history/medical records may be accessed that includes prior imaging and prior medical procedures.

8 ETHICAL AND REGULATORY CONSIDERATIONS

8.1 Potential Benefits

As stated in the PIS, the benefit to taking part in the study may be that the additional imaging performed may provide additional information to the radiologist that was not available in the clinical protocol. This is at the expense of spending up to an additional 15 minutes inside the scanner.

Furthermore, the PIS also reiterates that the information gathered in the study will help implement a protocol with DLR techniques aimed at reducing acquisition times and/or improving image quality.

This study will be performed according to the Declaration of Helsinki (1964) and with the approval from the local Research Ethics Committee (REC) before commencement of the study. Throughout this study, confidentiality will be maintained for both volunteer and patient alike, in accordance with the Data Protection Act (2018). For patients specifically, no additional information will be accessed that would not have been accessed as part of their routine rectum MRI scan/care.

8.2 Assessment and management of risk

There are no adverse events anticipated as part of this study as radiographers are specifically trained to screen patients and conduct MRI scans that minimise the risk of projectile effects, effects to implants, patient heating, acoustic noise and other bio-effects. The risks of these occurring during the study is no different to the routine clinical protocol that the patient was referred for. Additionally, Gadolinium-Based Contrast Agents (GBCAs) will not be given as part of the routine or study protocol. All risk assessments regarding the clinical use of MRI are stored locally within the MRI department.

To minimise the risk of safeguarding issues, patient participants will only be deemed suitable for participating in this study if they are not 'at-risk patients' and do not have any safeguarding alerts on the Hospital Information System (HIS). Any safeguarding issues that may arise will be dealt with according to the Trust's safeguarding policy. All researchers and members on the delegation log will have up-to-date safeguarding training, which is required by the trust and ensured via Mandatory and Statutory Training (MAST).

COVID-19 Risk Assessment and Management Strategy

All staff employed by SGUL and/or SGH NHS Foundation Trust are required to complete an ongoing COVID-19 risk assessment prior to undertaking any work on site, which includes research activity. This process is continuously monitored by the responsible line manager.

Participants (unaffected or affected) will not be recruited if they are deemed high risk or are in close contact with someone at risk. The Research Team will contact research participants ahead of scheduled study visits on-site to check for COVID-19 symptoms and the symptom check will be repeated when patients attend the hospital site for the study visit.

Participants will receive information regarding the extra precautions that will be taken in light of the COVID-19 pandemic in the Patient Information Sheet. This will detail steps that patients should take if they have concerns about exposure to COVID-19 through participating in the research, or believe that they are symptomatic or have been in close contact with another person believed to be symptomatic. The Patient Information Sheet will also have contact details for the Research Team for patients to get in touch if they have any concerns or queries about this.

All research personnel are expected to comply with the NHS Trust and University policies on COVID-19.

All patients attending the hospital site for research visits and/or routine clinical follow-up will be expected to abide by the NHS Trust and University policies on COVID-19 which include wearing

suitable PPE (provided by the NHS Trust on arrival), adhering to the visitor policy on social distancing and following the one-way routing systems whilst on site.

The schedule of study assessments has been designed so that they align with the current routine clinical pathway for this patient population

Therefore, research participants and site staff are not perceived to be at any additional risk of exposure to COVID-19 through participation in this research study.

